8.1.6 POST-TREATMENT ASSESSMENTS

8.1.6.1 END OF TREATMENT VISIT

If a subject permanently discontinues pembrolizumab, every attempt should be made to keep the subject in the study and continue to perform the required study-related follow-up and procedures.

The following procedures will be completed at the time of study treatment discontinuation for patients who elect to discontinue or are required to discontinue study treatment prior to the end of the planned study duration:

- Physical examination vital signs, including ECOG performance status
- Laboratory assessments and blood sampling:
 - Chemistry
 - TSH, T3, FT4
 - Hematology: CBC and differential
 - Assessment of adverse events
 - Recording of concomitant medications
 - Assessment of disease status if disease progression is suspected.

8.1.6.2 END OF STUDY VISIT (WEEK 104-105)

The following procedures will be completed at the end of study visit:

- Physical examination vital signs, including ECOG performance status
- Laboratory assessments and blood sampling:

- Chemistry
- TSH, T3, FT4
- Hematology: CBC and differential
- Assessment of adverse events
- Recording of concomitant medications

8.1.6.3 SAFETY FOLLOW-UP VISIT

The mandatory safety follow-up visit should be conducted approximately 30 days after the last dose of pembrolizumab treatment or before the initiation of a new anti-cancer treatment, whichever comes first. The safety follow-up visit can be done on the same day as the end of study visit (Section 8.1.6.2) or the end of treatment visit (Section 8.1.6.1). All AEs that occur prior to the safety follow-up visit should be recorded. Subjects with an AE of grade > 1 will be followed until the resolution of the AE to grade 0-1, or until the beginning of a new anti-cancer therapy, whichever occurs first. SAEs that occur within 90 days of the end of treatment or before initiation of a new anti-cancer treatment should also be followed and recorded.

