Briefly, patients will undergo baseline eligibility screening within 2 weeks prior to enrollment, including a medical history, physical examination, and assessment of performance status and hematology and chemistry parameters. Baseline assessment of disease status will be based on results of a bone marrow aspirate and biopsy for patients with AML and MDS, and a CT/PET scan (with a bone marrow exam for history of disease involvement) for patients with lymphoma. Baseline and subsequent bone marrow and peripheral blood samples will be obtained for correlative assays. Disease response assessment (bone marrow aspirate and biopsy and/or CT/PET) will be performed at baseline, and then every 3 months for 2 years, as well as any time if relapse is suspected. Specific procedures to be performed during the trial, as well as their prescribed times and associated visit windows, are outlined in the trial flow chart – Section 7.0. Details of each procedure are provided in Section 8.0 – trial procedures. After 24 months, ongoing disease re-assessments will be performed at the discretion of the treating physician. Any patient who experiences biopsy-proven disease progression at any time will be removed from study, and alternative treatment can be recommended at the treating physician's discretion. Subjects are not eligible for re-treatment on with pembrolizumab in the setting of this protocol should they experience a disease relapse after completing 24 months of therapy. After the end of treatment, each subject will be followed for 30 days for adverse event monitoring (serious adverse events will be collected for 90 days after the end of treatment). Subjects who discontinue treatment for reasons other than disease progression will have post-treatment follow-up for disease status until disease progression, initiating a non-study cancer treatment, withdrawal of consent, or becoming lost to follow-up. All subjects will be followed by telephone contact for overall survival until death, withdrawal of consent or the end of the study, whichever comes first.

The primary objective of this trial is to determine whether administration of pembrolizumab is tolerable in patients who have experienced disease relapse following alloSCT. Secondary objectives include analysis of efficacy parameters (ORR, DOR, OS). Correlative studies to examine the effect of PD-1 blockade therapy on T cell parameters and clonality, as well as on donor chimerism are planned as exploratory analyses.

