6.2.1 DOSE SELECTION/MODIFICATION

6.2.1.1 DOSE SELECTION (PREPARATION)

All subjects will receive 200 mg of pembrolizumab via IV infusion every 21 days. Details on preparation and administration are provided in the pharmacy manual.

The rationale for selection of pembrolizumab dose to be used in this trial is provided in Section 5.2. There are no specific clarifications or evaluations required to be performed in order to administer the proper dose to each subject.

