7.6 CYCLE 34 – POST TREATMENT

Trial Period				
Weeks of treatment/cycle#	100(D1C34)	103(D1C35)	End of Treatment***	Post-Treatment***
Scheduling Window (days):	(+/- 3)	(+/- 3)	(+/- 7)	(+/- 7)
Administrative Procedures				
Informed Consent				
Inclusion/Exclusion Criteria				
Demographics and Medical History				
Prior and Concomitant Medication Review				
Trial Treatment Administration	X	X		
Post-Study anticancer therapy status				X
Survival status	X	X	X	X
Clinical Procedures/Assessments				
Review Adverse Events	X	X	X	X
Full Physical Examination				
Directed Physical Examination	X	X	X	X
Vital signs and Weight	X	X	X	X
ECOG Performance Status	X	X	X	X
Laboratory Procedures/Assessments: analysis performed by local laboratory				
Pregnancy Test- Urine or Serum b-HCG				
PT/INR and aPTT				
CBC with differential	X	X	X	X
Comprehensive Serum Chemistry Panel	X	X	X	X
Urinalysis				

Trial Period				
Weeks of treatment/cycle#	100(D1C34)	103(D1C35)	End of Treatment***	Post-Treatment***
Scheduling Window (days):	(+/- 3)	(+/- 3)	(+/- 7)	(+/- 7)
T3, FT4, and TSH	X		X	X
HIV, CMV				
HBV core antibody, anti-HCV antibody				
Peripheral blood chimerism				X
Efficacy Measurements				
Tumor Imaging*				X
BM Biopsy**				X
Tumor Biopsies/Archival Tissue Collection Correlative Studies Blood				
Archival or Newly Obtained Tissue Collection				X
Correlative Studies Blood Collection				X

*Tumor imaging only for HL and NHL

**BM biopsy only for AML, MDS patients. For HL and NHL patients, a bone marrow is required only in patients with a prior history of marrow involvement

***The safety visit (Section 8.1.6.3) can be completed on the same date as the initial end of treatment or post-treatment visit. Follow-up visits should occur every 12 weeks until initiation of a new anti-cancer therapy, disease progression, withdrawal of consent or death, whichever comes first.

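### The safety follow-up visit may be merged with an earlier visit with no minimum interval from the last dose, so some non-serious adverse events in the 30-day window may go unrecorded

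*Combined protocol and SAP*

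**What the plan says.** Section 2.1 makes a general commitment, repeated in Section 6.8: "After the end of treatment, each subject will be followed for 30 days for adverse event monitoring". SAEs are collected for 90 days.

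Section 8.1.6.3 puts this into practice: "The mandatory safety follow-up visit should be conducted approximately 30 days after the last dose of pembrolizumab treatment", or before new anti-cancer treatment if that comes first. The same section then permits merging: "The safety follow-up visit can be done on the same day as the end of study visit (Section 8.1.6.2") or as the end-of-treatment visit of Section 8.1.6.1. The flow-chart footnote in Section 7.6 gives a similar permission: "The safety visit (Section 8.1.6.3) can be completed on the same date as the initial end of treatment or post-treatment visit". Neither place states a minimum interval from the last dose. Section 8.1.6.3 ties recording to the visit: "All AEs that occur prior to the safety follow-up visit should be recorded".

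The two visits it can be merged with are timed as follows:

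- Section 8.1.6.2 is headed "END OF STUDY VISIT (WEEK 104-105").
- Section 8.1.6.1 has no interval from the last dose: "The following procedures will be completed at the time of study treatment discontinuation".

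**The concern.** The 30-day commitment and the merge permission do not fit together. If the safety visit is moved forward to an earlier visit, the recording rule in Section 8.1.6.3 moves with it, and routine AE collection can close before day 30.

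Tolerability is the primary objective (Section 3.1), so complete AE capture matters more here than in an efficacy trial. The decision counts are also small. Section 9.1.1 halts the study at 5 or more DLTs in the first 12 patients and looks for at least 14 of 26 DLT-free. With such counts, one missed event could change a decision if it was a DLT.

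**Working it through.** **Inputs.** Dosing interval of 21 days (Section 6.2.1.1: "All subjects will receive 200 mg of pembrolizumab via IV infusion every 21 days"); last scheduled dose on day 1 of cycle 35, window ±3 days (Section 7.6); end-of-study visit in weeks 104–105 (Section 8.1.6.2); End of Treatment window ±7 days (Section 7.6); 30-day AE period (Sections 2.1, 6.8, 8.1.6.3). I count the 30 days from the last dose, as Section 8.1.6.3 does.

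**Reproducing the plan's own figure.** Week of cycle c = 1 + 3(c − 1). For c = 35 this gives 1 + 3 × 34 = week 103, as in the flow chart.

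**Patients completing 35 cycles.**

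1. Study day of the last dose = 1 + 21 × 34 = 715.
2. Week w runs from day 7(w − 1) + 1 to day 7w. Week 104 starts on 7 × 103 + 1 = day 722; week 105 ends on 7 × 105 = day 735.
3. Interval after the last dose: 722 − 715 = 7 days to 735 − 715 = 20 days.
4. Shortfall against 30 days: 30 − 20 = 10 to 30 − 7 = 23 days, that is 33% to 77% of the period.

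**Sensitivity to visit windows.** If the last dose shifts by ±3 days, the interval runs from 722 − 718 = 4 to 735 − 712 = 23 days, and the shortfall from 7 to 26 days. If the flow chart's +7 days is assumed to apply to the end-of-study visit, the latest nominal date is 20 + 7 = 27 days after the dose. Day 30 is reached only if the last dose is also 3 days early: 27 + 3 = 30.

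**Patients stopping early (illustrations, not figures in the plan).**

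- Last dose on day 1 of cycle 2 (day 22), stopped for progression at the next scheduled dosing visit (day 43). The 30 days end on day 52, so a merged visit loses 52 − 43 = 9 days. All of them lie within 90 days of starting treatment, the DLT window in Section 2.1.
- The same case with the visit 7 days later: 21 + 7 = 28 days after the dose, 2 days short.
- Discontinuation after a 12-week toxicity hold (Section 6.2.1.2): 84 days after the dose, well past day 30, so no shortfall.

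**Do other provisions close the gap?**

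| Provision | What it covers | Contact at about day 30? |
|---|---|---|
| 8.1.2.1 | AEs recorded during the study and follow-up | None specified |
| 7.6, 8.1.6.4 | AE review at post-treatment visits every 12 weeks; 8.1.6.4 limits these to patients who stop for reasons other than progression | No |
| 8.1.6.4.1 | Telephone contact every 12 weeks after progression or new therapy, for survival status | No |
| 8.2.3.1 | SAEs to 90 days, less if new therapy starts | Reporting duty only |
| 8.2.3.2 | ECIs, serious or not, to 90 days, less if new therapy starts | Reporting duty only |
| 8.1.6.3 | AEs above grade 1 followed to grade 0–1 | Does not clearly reach events that begin after a merged visit |

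What remains is a new AE, neither serious nor an ECI, that begins between a merged visit and day 30. It is most exposed in patients who have progressed, because their only scheduled contact is about survival.

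**The case against.** The strongest reply is that merging is optional, the visit remains mandatory at about 30 days, and the commitment in Sections 2.1 and 6.8 has no exception for merged visits. A site that follows those sections would still collect 30 days of AEs. Section 8.1.2.1 and the 12-weekly visits add further capture in patients who have not progressed. This stands, and it limits the conclusion to what may be missed. It does not remove the conflict, because Section 8.1.6.3 gives sites a permission and a recording cut-off that point the other way.

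A reader might infer more than the text supports:

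- **That AEs in the window will not be recorded, or that only SAEs continue to 90 days.** ECIs, including non-serious ones, also run to 90 days within their limits.
- **That grade 2 immune-related events are lost first.** Section 5.3 designates immune-related AEs of grade 2 or higher as events of clinical interest. Whether each of these, or grade 2 GVHD, falls under the 90-day rule depends on a guidance document that is not in the file. GVHD is not in the list printed in Section 8.2.3.2.
- **That every end-of-treatment visit is early.** It is not tied to the last dose and can fall after day 30. The footnote also allows merging with the initial post-treatment visit, which need not be early.
- **That the 10 to 23 days affect the primary endpoint.** For completers they lie outside both the 90-day DLT window and the end-of-treatment assessment in Section 9.2.4.1. Only early stoppers can lose days inside the DLT window.
- **That merging makes AE rates non-comparable within the trial.** Follow-up already varies by design, because the safety visit moves forward when new therapy starts. There is one arm and no between-arm comparison.

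**Conclusion.** The point holds as an inconsistency that should be corrected. The merge permission carries no minimum interval, and recording is tied to the visit. At weeks 104–105 a merged visit comes nominally 7 to 20 days after the last dose, so 10 to 23 of the 30 promised days may go without routine AE recording. For end-of-treatment visits the shortfall depends on when the patient stops and may be nil.

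The exposure is confined to new AEs that are neither serious nor ECIs, mainly in patients who stop for progression. The possible effect on the primary endpoint is limited to early stoppers who have an unrecorded, non-serious DLT-grade event in those days. The documents give no rate for such events, so I put no number on how many would be missed.

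The conclusion assumes that sites use the permission, that day 715 is the actual last dose, and that the 30 days run from that dose. No sample size, power or error rate is affected.

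**What to change.** In Section 8.1.6.3 and the flow-chart footnote, allow merging only when the combined visit is about 30 days or more after the last dose, or when new anti-cancer treatment is about to start. Otherwise keep the earlier visit and add a telephone AE contact at about day 30, including for patients who have progressed. For a completer on schedule this falls at about study day 715 + 30 = 745.

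Replace the visit-based recording rule with a date-based one: *all AEs through 30 days after the last dose or until the start of new anti-cancer treatment, whichever comes first*. The new-treatment limit should stay, because Sections 8.1.1.5.3 and 8.1.6.3 already rely on it. Leave the SAE and ECI reporting periods as they are. Reconcile Sections 2.1, 6.8, 7.6, 8.1.2.1 and 8.1.6.3 with the new wording.

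The cost is a short wording change and at most one telephone contact per patient, so no more than 26 calls at full enrolment.

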8.1.6.4 FOLLOW-UP VISITS

Subjects who discontinue trial treatment for a reason other than disease progression will move into the follow-up phase and should be assessed every 12 weeks (+/- 7 days) to monitor disease status. Every effort should be made to collect information regarding disease status until the start of new anti-cancer therapy, disease progression, death, or end of the study. Information regarding post-study anti-cancer treatment will be collected if new treatment is initiated.

8.1.6.4.1 SURVIVAL FOLLOW-UP

Once a subject experiences confirmed disease progression or starts a new antineoplastic therapy, the subject moves into the survival follow-up phase and should be contacted by telephone every 12 weeks to assess for survival status until death, withdrawal of consent, or the end of the study, whichever occurs first.

8.2 ASSESSING AND RECORDING ADVERSE EVENTS

The rate of subject entry and expansion will depend upon assessment of the safety profile of patients entered at the previous dose level. Toxicity will be evaluated according to the NCI Common Terminology Criteria for Adverse Events (CTCAE), Version 4.0 (see Appendix E). If at least 5 of the first 12 patients complete pembrolizumab treatment without developing a DLT, we will open an expansion cohort to enroll with plans to enroll 14 additional patients should DLT-associated stopping rule not be met in the first 12 patients. If at least 14 of the 26 patients remain DLT-free, we would have sufficient

evidence to warrant further study of pembrolizumab in a future trial.

This particular safety stopping rule is based on the expected 50% rate of GVHD that has been reported to develop after DLI therapy³⁰. The inclusion of an expansion cohort will enable a further and more robust safety signal, as well as provide a larger cohort of patients in whom to assess clinical response, especially given the mixture of diseases that are being included in this study.

8.2.1 DEFINITION OF AN OVERDOSE FOR THIS PROTOCOL AND REPORTING OF OVERDOSE TO THE SPONSOR

For purposes of this trial, an overdose will be defined as any dose exceeding the prescribed dose for pembrolizumab will be defined as any dose of 1000 mg or greater. No specific information is available on the treatment of overdose of pembrolizumab. In the event of overdose, pembrolizumab should be discontinued and the subject should be observed closely for signs of toxicity. Appropriate supportive treatment should be provided if clinically indicated.

If an adverse event(s) is associated with (“results from”) the overdose of pembrolizumab, the adverse event(s) is reported as a serious adverse event, even if no other seriousness criteria are met.

If a dose of pembrolizumab according to the definition of overdose is administered without any associated clinical symptoms or abnormal laboratory results, the overdose is reported as a non-serious Event of Clinical Interest (ECI), using the terminology “accidental or intentional overdose without adverse effect.”

All reports of overdose with and without an adverse event must be reported within 24 hours to the sponsor either by electronic media or paper.

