Acute GVHD is influenced by factors that either positively or negatively modulate donor T cell activation, and the PD-1/PD-L1 pathway has been previously implicated in exacerbating acute GVHD in pre-clinical models. For example, in a MHC-mismatched murine alloSCT model, acute GVHD was enhanced in transplant recipients treated with a PD-L1 blocking antibody²³. Additional studies in animals have found elevated expression of PD-L1 and PD-L2 in GVHD target organs following alloSCT. Interestingly, PD-1/PD-L1, but not PD-1/PD-L2 blockade markedly accelerated GVHD-related lethality²⁴. Although PD-1 blockade has not formally been tested in humans in the post-transplant setting, results in animal models do raise concern that by attempting to harness a GVT effect via PD-1 blockade, GVHD could develop as a complicating factor. In addition, a recent presentation at the 2015 meeting of the American Society of Hematology, Herbeux and colleagues presented a retrospective analysis of nivolumab treatment for patients with Hodgkin lymphoma who had relapsed following alloSCT. Of 8 evaluable patients, acute GVHD occurred in 2 (grades 3 and 4 acute GVHD of the skin). Both patients had a history of acute GVHD in the 3 months prior to receiving nivolumab. Seven of 8 nivolumab-treated patients derived clinical benefit, with 4 achieving a partial response (PR), and 3 a complete response (CR). Furthermore, both patients who developed GVHD improved with treatment²⁵.

4.4 POST-ALLOSCT IMMUNOTHERAPY.

Unfortunately, patients who relapse after alloSCT have few treatment options and dismal outcomes. Withdrawal of immunosuppression to unleash a GVT effect has been effective in CML, but rarely in other diseases²⁶. Chemotherapy may be an option, although responses are not often durable²⁷, and most patients do not have sufficient performance status or hematological reserve to tolerate cytotoxic therapies. Cellular-based immunotherapies, including donor lymphocyte infusion (DLI), as well as adoptive T and NK cell therapy, have been employed to treat disease relapse following allo-SCT with

variable efficacies^{28, 29, 30}, including a 2-year survival of only 21% following DLI in an EBMT study³¹. In addition, acute GVHD develops in up to 40–60% of patients who receive DLI, and pancytopenia, infections, current GVHD, and donor availability at the time of relapse are major impediments to its use^{30, 31}.

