9.2.4 STATISTICAL METHODS

9.2.4.1 STATISTICAL METHODS FOR TOLERABILITY ANALYSES

The trial will feature a two-stage minimax trial design (Simon 1989, A'hern, 2001) which tests for futility in a smaller sample of patients before proceeding with treatment of the full cohort. The accrual rate will be 1 patient/month in relapsed/refractory myeloid and B cell malignancies following allogeneic stem cell transplant to assess the safety and feasibility of pembrolizumab. The primary outcome is whether the patient remains DLT-free at the end of treatment. *A priori*, we expect 40% or fewer patients on an unsafe treatment would finish without experiencing a DLT, and at least 65% of patients would be DLT-free on a safe treatment. For $\alpha = 0.05$ and 80% power, we would need to observe

at least 5 DLT-free treatments out of a small sub-sample of 12 patients before we would consider evaluating pembrolizumab in the full sample of 26 patients. If at least 14 of the 26 patients respond remain DLT-free, we would have sufficient evidence to warrant further study of pembrolizumab in a future trial.

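### The 50% GVHD-after-DLI figure given as the basis of the safety rule is not the basis of the tested threshold (60% versus 35% DLT), and a pass does not show a DLT rate below 50%.

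*Combined protocol and SAP*

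**What the plan says.** Section 8.2 sets out the two-stage rule (at least 5 of 12, then at least 14 of 26, DLT-free) and then gives its rationale: "This particular safety stopping rule is based on the expected 50% rate of GVHD that has been reported to develop after DLI therapy". The background, Section 4.4, has the related statement that "acute GVHD develops in up to 40–60% of patients who receive DLI". Neither place gives a GVHD grade.

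The hypothesis is in Section 9.2.4.1: "The trial will feature a two-stage minimax trial design". The unsafe case is put as "we expect 40% or fewer patients on an unsafe treatment would finish without experiencing a DLT". For the safe case, the same section assumes that "at least 65% of patients would be DLT-free on a safe treatment". With alpha 0.05 and 80% power, it asks for "at least 5 DLT-free treatments out of a small sub-sample of 12 patients" before "evaluating pembrolizumab in the full sample of 26 patients", and for at least 14 DLT-free at the end. That section mentions neither DLI nor 50%.

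Section 2.1 defines the DLT: grade 3 or 4 acute GVHD, graft rejection, unexpected related toxicity above grade 2, or immune-related vital-organ dysfunction above grade 2. Grade 2 acute GVHD is a treatment-limiting toxicity and is not counted.

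Sections 9.1.1 and 9.1.3 add a different stage 1 rule: the trial halts if 5 or more of the first 12 patients have a DLT.

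**The concern.** Apart from the background range, the sentence in 8.2 is the only reason the documents give for where the tolerability threshold sits, and it does not match the design in two respects.

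- **Level.** The figure cited is 50%. The null is a 60% DLT rate and the alternative 35%.
- **Endpoint.** The figure cited is GVHD of unstated grade. The DLT leaves out grade 2 acute GVHD and adds events that are not GVHD. A GVHD rate of unknown grade cannot by itself justify a 60% ceiling on such a composite. The documents give no rate of severe GVHD after DLI.

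What is at stake is how a pass is read. It is the stated trigger for further study, and the primary hypothesis turns on an acceptable incidence of immune-related events. Someone who takes the rationale at face value may think that a pass places toxicity below 50%. The cut-offs do not establish that.

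**Working it through.** **Inputs.** From 9.2.4.1: p0 = 0.40 and p1 = 0.65 DLT-free, alpha 0.05, power 0.80, n1 = 12, N = 26, printed cut-offs 5 and 14. From 9.1.1 and 9.1.3: halt at 5 or more DLTs in 12. At most 4 DLTs then allow continuation, so at least 12 − 4 = 8 must be DLT-free.

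**Formula.** With stage 1 cut-off a1, final cut-off a and true DLT-free probability p,

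P(pass) = Σ (x = a1 to 12) C(12,x) p^x (1−p)^(12−x) × P(Y ≥ a − x), with Y ~ Bin(14, p).

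**Step 1: reproduce the plan's design.** An exact search for the Simon minimax design at 0.40 versus 0.65 (one-sided alpha 0.05, power 0.80) gives n1 = 12, r1 = 5, N = 26, r = 14, with alpha 0.0469 and power 0.8086. The sample sizes of 12 and 26 reproduce, so the design comes from the 60% and 35% DLT rates and not from 50%. In Simon's notation r1 and r are the largest failing counts. The cut-offs that go with this design are therefore at least 6 of 12 and at least 15 of 26, one above those printed.

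**Step 2: pass probability by rule.**

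| DLT-free needed | DLT rate 60% (type I error) | DLT rate 50% | DLT rate 35% (power) |
|---|---|---|---|
| ≥5/12, ≥14/26 (as printed) | 0.104 | 0.410 | 0.907 |
| ≥6/12, ≥15/26 | 0.047 | 0.257 | 0.809 |
| ≥8/12 (halt rule), ≥14/26 | 0.033 | 0.163 | 0.576 |
| ≥8/12 (halt rule), ≥15/26 | 0.021 | 0.133 | 0.560 |

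A cross-check on 0.410: ignoring stage 1, P(at least 14 of 26) at p = 0.50 is 0.423, and the stage 1 look removes about 0.013.

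**Step 3: what a pass shows.** The lowest passing result is 14 DLT-free, so 26 − 14 = 12 DLTs, and 12/26 = 46.2%. The exact (Clopper-Pearson) 95% CI is 26.6% to 66.6%, and the one-sided 95% upper limit is 63.8%. At 15 DLT-free (11/26 = 42.3%) the one-sided upper limit is 60.2%. At 17 DLT-free it is 52.6%. At 18 DLT-free (8/26 = 30.8%) it is 48.7%, the first result to exclude 50% one-sided. These intervals treat 26 as a fixed sample and ignore the stage 1 look.

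**Step 4: left out.** Sections 9.1.1 and 9.1.3 also close the trial if each of the first 5 patients has severe GVHD. At a 50% DLT rate that has probability at most 0.5^5 = 0.031, and it can only lower the figures in the table.

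**The case against.** Several points on the other side are fair.

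- **Section 8.2 says the rule is based on 50%, not that 50% is the null.** The figure lies between the 60% null and the 35% alternative, and the upper end of the 40–60% range in 4.4 equals the null. A loose link is possible. This stands as far as it goes, but no section explains the link, and the endpoint difference remains wherever 50% is placed.
- **The plan never claims a comparison with DLI.** A reader might infer that a pass is meant to show pembrolizumab to be safer than DLI. The documents do not say so. Sections 8.2, 9.1.1 and 9.2.4.1 conclude only that further study would be warranted, and this is an uncontrolled pilot.
- **Evaluating the rule at a 50% DLT rate mixes two endpoints.** A reader might take 0.41 as the error rate against the DLI benchmark. It is not. It describes the rule at one DLT rate between null and alternative, and it applies only to the printed cut-offs. With the halt in 9.1.1 and 9.1.3 it falls to 0.16 or 0.13.
- **A reader might also infer that the null should have been 50% and the trial is too small.** Keeping 80% power at 65% DLT-free against 50% would need 68 patients. The documents do not commit to that null, so no resizing follows.
- **That the just-passing interval covers 60% is partly a separate matter.** It reflects cut-offs printed one too low and a two-sided interval set against a one-sided design. This is correct, and it is not evidence of the benchmark mismatch.

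**Conclusion.** The point holds as a mismatch between stated rationale and tested design. The 50% figure is not what the threshold was built on: n = 12 and N = 26 reproduce from 60% versus 35% DLT, and the endpoint is not the one the 50% describes. A pass does not show a DLT rate below 50%. At a true 50% DLT rate the pass probability is 0.13 to 0.41, depending on which stage 1 rule and final cut-off apply.

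Even the more modest statement, that a pass is evidence against a 60% DLT rate, is not supported at alpha 0.05 with the printed cut-offs, where the exact type I error is 0.104.

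The figures assume independent patients with one yes/no DLT outcome each and a common DLT probability across diseases. The grade behind the 50% lies in a cited source and is not known here. The sample size is not in question.

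**What to change.** 1. In 8.2, replace the DLI sentence with the rates the design uses: a 60% DLT rate as unsafe and 35% as safe.
2. Reconcile the stage 1 passages. Sections 8.2, 9.1.1 and 9.2.4.1 continue with 5 or more DLT-free of 12 (up to 7 DLTs). Sections 9.1.1 and 9.1.3 halt at 5 or more DLTs.
3. In 9.2.4.1, for the cut-offs finally kept, state the exact type I error at 60%, the power at 35% and the pass probability at a 50% DLT rate. For reference, the printed cut-offs give 0.104, 0.91 and 0.41. At least 6/12 and at least 15/26 give 0.047, 0.81 and 0.26.
4. Describe a pass as evidence against a 60% DLT rate only at that actual alpha. Report the observed DLT rate with its exact 95% CI, and do not present it against the DLI figure.

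Steps 1, 3 and 4 are text only, and no step adds patients. The price is a less favourable stated conclusion. If the halt at 5 or more DLTs is retained, power at a 35% DLT rate is 0.58 or 0.56 and not the planned 80%, and the plan would have to say so.
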